| | for the Nexus-D2 substudy will have the option for data downloading and |
| | Tor the Nexus-D2 substudy will have the option for data dowinioading and |

| | operant conditioning at home. The goal of the operant conditioning is to |
|--------------------|--|
| | evaluate whether PD patient practice in modulating brain activity may lead to |
| | clinical improvement of PD symptoms |
| | |
| Objectives | In fifteen patients undergoing DBS implantation for PD or primary dystonia (10 PD; 5 dystonia), we will implant a unilateral subdural cortical electrode in addition to the DBS electrode, and connect these to a novel implantable pulse generator that can store field potential data (Medtronic Activa PC+S). At multiple time points post-implantation in our clinic, we will record and download cortical and basal ganglia LFPs on and off of DBS therapy in the following behavioral conditions: a.) rest b.) during a computer controlled binary choice arm reaching task c.) walking up and down a hallway Hypotheses: Long term recording of cortical LFPS is technically feasible with stable signals over 1 year, without adverse events 2) Chronic (6 and 12 months) basal ganglia DBS alters the spectral characteristics of the M1 LFP (spectral power in beta and gamma bands), the magnitude of movement related M1 beta band change, and the coupling between beta rhythms and broadband gamma activity. We expect that in PD, DBS-induced changes will appear in early recordings |
| | (immediately after starting DBS), whereas in primary dystonia, cortical |
| | changes will be seen only after long-term DBS. |
| | 3) DBS-induced changes in abnormal cortical oscillatory activity may predict the degree of DBS-induced improvement in motor function |
| | Markers of abnormal cortical or basal ganglia oscillatory activity can help determine clinically effective stimulation settings. |
| Patient Population | Study subjects will be adults with Parkinson's disease (PD) or primary dystonia, recruited from a clinic population of patients scheduled to undergo unilateral or bilateral DBS implantation for amelioration of their movement disorder symptoms. |
| Sample Size | 15 subjects |
| Efficacy | Clinical rating scales of motor function: |
| Assessments | For PD patients: Unified Parkinson's Disease Rating Scale (UPDRS) parts I-IV and |
| | dyskinesia rating scales. UPDRS part III will be scored on and off of |
| | antiparkinsonian medications. For dystonia patients: Burke-Fahn Marsden |

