| | Dystonia Rating Scale (BFMDRS) and Toronto Western Spasmodic Torticollis |
| | rating scale (TWSTRS). |
| | Other rating scales (all patients): Clinician Global Impression of Change (CGI-C) |
| C . (.) | and Patient Global Impression of Change (PGI-C). |
| Safety | 1)Physical examination at all study visits |
| Assessments | 2) Check of pulse generator stimulation parameters, impedance measurements, |
| | and battery voltage at all study visits |
| | 3) Surgical or nonsurgical protocol-defined adverse events as recorded on |
| | adverse events case report forms4) Assessment of suicidality using the Columbia Suicide Severity Rating Scale, at |
| | all protocol-defined outpatient visits |
| | |

| 5) In visits where the Nexus will be used for closed loop stimulation, all possible |
|---|
| stimulation settings are preselected by clinicians to avoid the possibility of |
| producing major stimulation-induced adverse effects |

Statistical Methods and Data Analysis

ECoG and LFP data will be analyzed in the frequency domain for mean log power in the beta and gamma bands, movement related changes in beta and gamma band power, and coupling between low frequency rhythms and broadband gamma power (12, 20, 21). Using a repeated measures ANOVA statistical analysis, summary statistics for power in relevant frequency bands, movement related power changes, and indices of phase-amplitude coupling will be compared at different time points, different DBS conditions (on and off), and different disease states (PD or primary dystonia).

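### Hypothesis 2 attributes late cortical change to long-term DBS, but stimulation is analysed only as on or off and recorded settings go unused, so a change in settings could be read as a chronic effect

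*Combined protocol and SAP*

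**What the plan says.** All references are to the Protocol Synopsis.

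- **Objectives, hypothesis 2.** The claim concerns duration: "Chronic (6 and 12 months) basal ganglia DBS alters the spectral characteristics of the M1 LFP". The early part reads "We expect that in PD, DBS-induced changes will appear in early recordings", defined as immediately after stimulation begins. For dystonia the prediction is that cortical "changes will be seen only after long-term DBS".
- **Objectives, recordings.** At several visits "we will record and download cortical and basal ganglia LFPs on and off of DBS therapy". The settings to be used for the on-DBS recording are not stated.
- **Statistical Methods and Data Analysis.** The repeated measures ANOVA compares "different time points, different DBS conditions (on and off), and different disease states (PD or primary dystonia". It has no term for stimulation settings.
- **Safety Assessments, item 2.** "Check of pulse generator stimulation parameters, impedance measurements" and battery voltage are covered at all study visits, but these data appear only as a safety item.
- **Objectives, final hypothesis.** "Markers of abnormal cortical or basal ganglia oscillatory activity can help determine clinically effective stimulation settings". The add-on question in the statistical section likewise asks about settings that minimise synchronization. The plan itself therefore expects the recorded signal to depend on settings.

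**The concern.** An on-DBS recording reflects the stimulation delivered when it was made. If amplitude, contact, pulse width or frequency differs between the first recording and the one at 12 months, the on-minus-off contrast can change with no effect of long exposure. Subtracting the off recording removes drift common to both states. It does not remove a change in what the on state delivered.

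Time is a factor in the ANOVA, so the early and late on recordings are separate cells. Nothing in the model, however, says why those cells differ. A late rise in dystonia would be read as support for hypothesis 2. If the two diseases are adjusted differently, the time-by-disease comparison is affected as well: rising PD settings, for example, would blur the predicted contrast. The study is meant to frame hypotheses about mechanism for the next phase, so a misattributed late effect could steer that choice.

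**Working it through.** **No figure to reproduce.** The plan gives no alpha, effect size, SD or power, and states that there is no formal sample size calculation. The size below is an illustration.

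**Input from the documents:** 5 dystonia patients (Objectives).

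**Assumptions, not in the documents:** two-sided 5% tests; no true chronic effect; on-minus-off effect proportional to delivered stimulus; early mean effect *d* = 1.0 or 1.5, in units of the SD of the within-patient change; stimulus raised by a fraction *g* = 0, 0.5 or 1.0, the same in every patient; visit-to-visit correlation ρ = 0 or 0.5.

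**Step 1. Model.** Let E1 and E2 be a patient's on-minus-off effect at first stimulation and at 12 months, and D = E2 − E1.
- Mean E1 = *d*; mean E2 = *d*(1 + *g*); mean D = *d* × *g*.
- SD(D) = 1, so SD(E1) = SD(E2) = 1/√[2(1 − ρ)], which is 0.71 at ρ = 0 and 1.00 at ρ = 0.5.

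**Step 2. Any later increase.** A one-sample t-test of D with n = 5 has noncentrality *d* × *g* × √5.
- *g* = 0.5: shift 0.5 to 0.75 SD, rejection 14% to 25%.
- *g* = 1.0: shift 1.0 to 1.5 SD, rejection 40% to 71%.

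These rates count every late increase, including cases where an early effect is already evident. That is not the dystonia prediction.

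**Step 3. The predicted pattern.** Late-only means that E1 is not significant (|t| ≤ 2.776 on 4 df) and D is significantly positive (t > 2.776). With 200,000 simulated trials per cell:

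| *d* | ρ | unchanged | 50% higher | doubled |
|---|---|---|---|---|
| 1.0 | 0 | 1.4% | 6.4% | 15.6% |
| 1.0 | 0.5 | 1.9% | 9.9% | 26.5% |
| 1.5 | 0 | 0.3% | 2.0% | 4.8% |
| 1.5 | 0.5 | 1.2% | 9.3% | 21.9% |

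The ranges are about 0.3% to 2%, 2% to 10% and 5% to 27%.

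**Step 4. Boundary case.** If the early effect is truly zero (*d* = 0), proportionality keeps it at zero at any setting, and the late-only rate stays near 2%. Settings alone then produce a late effect only through a threshold or other nonlinear response, which is not modelled here.

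**Step 5. Covariate adjustment.** Regressing D on the change in settings in 5 patients uses an intercept and a slope, leaving 5 − 2 = 3 residual degrees of freedom.

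**The case against.** The strongest reply has four parts.

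1. **No passage says that settings change.** Listing programmers shows only that the devices can be programmed, and the closed-loop add-on is optional. This stands: the point is about what could happen. Equally, no passage holds settings constant, and the analysis would not reveal a change.
2. **Off-DBS recordings enter the same ANOVA.** A change across them is not directly driven by the settings active during recording. This also stands, although carry-over from earlier stimulation may remain, and the plan does not name that contrast as the test of hypothesis 2.
3. **This is a declared exploratory pilot, described in a synopsis.** That limits how firmly anything will be concluded and makes silence weaker evidence. It does not remove the ambiguity in the comparison the plan does describe.
4. **Adjusting for settings is a poor cure.** Settings are chosen after baseline, possibly in response to symptoms or, in the add-on, to the brain signal itself. With 3 residual degrees of freedom the model would have little power and could add bias. This stands and shapes the fix.

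A reader might infer that time and stimulus are completely mixed and that the trial cannot tell longer from more stimulation. The documents do not support that: off-DBS recordings exist, and settings may change differently between patients, so the data can partly separate the two. A reader might also take the rates for any late increase, or the corresponding PD rates, as the size of the problem. The former overstate it, because they include patterns that contradict a late-only effect. The latter do not bear on it, because the plan predicts early change in PD.

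**Conclusion.** The concern holds in a limited form. Hypothesis 2 is about duration of exposure, stimulation enters the analysis only as on or off, and settings are neither fixed across recordings nor used. A settings change could therefore be reported as a chronic-exposure effect or could obscure the disease contrast. Under the stated assumptions the false late-only dystonia rate rises from at most about 2% to about 2% to 10% with a 50% higher stimulus, and to 5% to 27% with a doubled one. The real size is unknown: it depends on how far settings move and on how the signal responds, and the documents give neither. The issue affects what may be concluded about mechanism; the feasibility goal is untouched.

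**What to change.** Add to Statistical Methods and Data Analysis:

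1. Link to each on-DBS recording the settings and impedance already checked at that visit, for the PC+S side (the side carrying the cortical electrode). Tabulate them by visit and disease.
2. For hypothesis 2, report beside the planned ANOVA:
   - (a) the time effect in visit pairs with unchanged contact and settings, descriptively;
   - (b) the change across off-DBS recordings, noting that carry-over may remain.
3. Treat any model adjusted for settings as exploratory only.
4. Describe a late change as a chronic-exposure effect only if (a) or (b) shows it in the same direction. Otherwise report that time and stimulation change are not separable. Agreement in direction is a minimum condition, not proof, with so few patients.

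The cost is a data link from the safety form to the recordings and a little more analysis. Some patients may have few or no unchanged-settings pairs, and the conclusion may be more cautious. No new visit or measurement is needed, and how patients are programmed does not change.

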Although the sample size is small, in each disease group we will assess the correlation between these brain physiology measures, and clinical instruments used to measure the motor benefit produced by DBS. In particular we will ask: 1) Did the degree of cortical synchronization, as assessed by a quantitative index of phase-amplitude coupling (PAC) prior to starting stimulation therapy, correlate with the degree of benefit produced by DBS (difference between clinical ratings at 12 months on stimulation and baseline pre-implantation, off medication). 2) Did the magnitude of DBS-induced suppression of cortical synchronization (difference between PAC on-stimulation at 12 months, versus prior to starting stimulation therapy) correlate with the degree of benefit produced by DBS (difference between PAC on-stimulation, off medication) 3) For the add-on study examining potential therapeutic uses of Activa PC+S: 1) Did the DBS stimulation settings which minimized metrics of cortical synchronization or basal ganglia synchronization, produce a therapeutic benefit compared with the off stimulation and off medication state; and 2) Did operant control of cortical or basal ganglia rhythms produce a therapeutic benefit compared with the off stimulation and off medication state; and off medication state prior to learning operant control.

Since this is a pilot study of chronic cortical recording, the sample size is likely to be too small to provide definitive answers to all research questions. Based on this exploratory analysis, it is anticipated that the next phase of the study will focus on a subset of the research aims, with 10-15 subjects per group.

Sample size calculation: This is a pilot study of a novel chronic brain recording technique. The goals are to assess technique feasibility, to collect pilot data that will be used to frame more detailed hypothesis about DBS mechanisms, and (in the add-on study using Nexus-D) to explore potential strategies for therapeutic use of the Activa PC+S neural interface. Thus, there is no formal sample size calculation.

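### Correlation question 2 defines clinical benefit as a PAC difference, and labels a one-year PAC change as DBS-induced without using a 12-month off-stimulation recording

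*Combined protocol and SAP*

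**What the plan says.** The plan is a single combined protocol synopsis and SAP. In Statistical Methods and Data Analysis, the correlation analyses are run within each disease group and relate brain physiology measures to the "clinical instruments used to measure the motor benefit produced by DBS".

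- Question 1 defines benefit as the "difference between clinical ratings at 12 months on stimulation and baseline pre-implantation, off medication".
- Question 2 takes as its physiological variable the "magnitude of DBS-induced suppression of cortical synchronization (difference between PAC on-stimulation at 12 months, versus prior to starting stimulation therapy") and correlates it with the "degree of benefit produced by DBS (difference between PAC on-stimulation, off medication").

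Under Objectives, hypothesis 3, which question 2 serves, is that "DBS-induced changes in abnormal cortical oscillatory activity may predict the degree of DBS-induced improvement in motor function". Hypothesis 1 is that "Long term recording of cortical LFPS is technically feasible with stable signals over 1 year, without adverse events". The same section says that, at multiple time points after implantation, "we will record and download cortical and basal ganglia LFPs on and off of DBS therapy". The repeated measures ANOVA in the statistical section includes time point, DBS condition (on or off) and disease.

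The statistical section calls the analysis exploratory and expects, on the strength of it, that "the next phase of the study will focus on a subset of the research aims".

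**The concern.** There are two separate problems in one sentence of the plan.

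**Outcome.** The benefit variable in question 2 is given as a PAC quantity. An analyst following the text would correlate one PAC difference with another and would not learn whether cortical change tracks motor improvement.

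**Attribution.** The physiological variable is called DBS-induced but is a before-and-after difference about a year apart, with no unstimulated control group. It holds the DBS effect plus whatever else changed in the recorded signal. The plan cannot take that remainder as zero, because signal stability over one year is one of its own hypotheses. An off recording at the 12-month visit would show how much of the change depends on stimulation being on at that moment, but question 2 does not use one.

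At stake is the choice of aims for the next phase. A correlation weakened or produced by drift could steer that choice wrongly.

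**Working it through.** The plan states no alpha, power, effect size or SD, and says there is no formal sample size calculation, so there is no figure to reproduce.

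**Part (a): the benefit definition, side by side**

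| Place | What benefit means |
|---|---|
| Objectives, hypothesis 3 | Improvement in motor function |
| Sentence introducing the correlations | Motor benefit measured by clinical instruments |
| Question 1 | Clinical ratings, 12 months on stimulation versus pre-implantation baseline |
| Question 2 | A PAC difference, with no comparator or time point |

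Three places agree and question 2 departs from them. No arithmetic is needed.

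**Part (b): what the PAC change contains**

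Let A be the DBS effect present only while stimulation is on, L the effect that persists when it is off, and G any other change over the year. If G enters both 12-month recordings equally:

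- on at 12 months − pre-stimulation = A + L + G
- on at 12 months − off at 12 months = A
- off at 12 months − pre-stimulation = L + G

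The last two sum to the first. A proportional change in signal would still rescale A.

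*From the plan:* n = 10 (PD) and n = 5 (dystonia), analysed separately. *Assumed:* true correlation of 0.7 between D = A + L and clinical benefit; A and L independent; D has variance 1; G is independent of D with SD k = 0.5 or 1.0; normal data; two-sided 0.05 Pearson test. Power is from 400,000 simulated trials per cell, except in step 2 (200,000).

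1. *Drift unrelated to benefit:* r = 0.7/√(1 + k²).

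| k | r | Power, n = 10 | Power, n = 5 |
|---|---|---|---|
| 0 | 0.70 | 68% | 27% |
| 0.5 | 0.7/√1.25 = 0.63 | 53% | 20% |
| 1.0 | 0.7/√2 = 0.49 | 32% | 13% |

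2. *Drift correlated 0.5 with benefit:* r = (0.7 + 0.5k)/√(1 + k²). At k = 0.5, 0.95/1.118 = 0.85; at k = 1.0, 1.20/1.414 = 0.85. With no true link between D and benefit, r = 0.5k/√(1 + k²) = 0.22 or 0.35, and the test at n = 10 is significant in 9% or 17% of trials.

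3. *Drift identical in every patient:* a constant added to all values leaves r unchanged.

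4. *On minus off alone:* with a lasting share f of the effect variance, r = 0.7√(1 − f). At f = 0.25, 0.50 and 0.75 this is 0.61, 0.49 and 0.35, with power at n = 10 of 50%, 32% and 17%. Against step 1 it breaks even where 1 − f = 1/(1 + k²), so f = k²/(1 + k²): 0.25/1.25 = 20% at k = 0.5 and 1/2 = 50% at k = 1.0. With recording noise of variance v in each recording, the break-even solves (1 − f)²/(1 − f + 2v) = 1/(1 + k² + 2v). At an assumed v = 0.25, f = 11% and 31%; at v = 0.5, 8% and 23%.

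5. *Precision:* the Fisher z interval for an observed r of 0.7 is tanh(0.867 ± 1.96/√(n − 3)): 0.13 to 0.92 at n = 10 and −0.48 to 0.98 at n = 5.

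**The case against.** The strongest reply is that the existing contrast fits the question. Benefit in question 1 is a change over about the same year, and hypothesis 2 expects cortical change in dystonia only after long-term DBS. Same-visit on minus off would miss whatever persists off stimulation. This stands. A reader might infer that the contrast is wrong and should be replaced; the documents do not support that, and step 4 shows that on minus off often has less power.

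A reader might also infer that the plan ignores off-stimulation data. It does not: the pre-stimulation recording is itself off stimulation, and the ANOVA already compares on and off at group level. The gap is narrower. The patient-level correlation uses no off recording from the 12-month visit. The impedance checks planned at all study visits bear on electrode stability, but they do not enter question 2 and do not separate drift from DBS effect.

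It is tempting to say that drift can only weaken the correlation. That holds only if drift is unrelated to benefit, which the documents do not establish.

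Finally, the PAC wording in the benefit definition is probably a drafting slip. That is likely, but the text still needs correcting. One might go further and put a size on the spurious correlation from the literal wording. The definition gives no comparator or time point, so any such figure would rest on an invented one.

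**Conclusion.** The point holds in two parts of different weight.

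(a) The benefit definition in question 2 is wrong as written. It conflicts with the plan's own introductory sentence, question 1 and hypothesis 3. This rests on the text alone.

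(b) The attribution issue is an inexpensive improvement. The label assumes stable signals, which the study sets out to test. Patient-specific drift can move the correlation either way: from 0.70 down to 0.63 or 0.49, or up to 0.85, under the assumptions above. The documents give no basis for the real size or direction.

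This is a matter of attribution and labelling in a pilot that already says its sample is likely too small for definitive answers. It is worth considering and does not threaten the study.

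**What to change.** 1. In question 2, define benefit as in question 1: clinical ratings at 12 months on stimulation versus the pre-implantation baseline, off medication.
2. Keep the present PAC contrast and rename it change from pre-stimulation.
3. Report beside it, within each disease, 12-month on minus off and 12-month off minus pre-stimulation, each correlated with clinical benefit and given with a 95% CI.
4. State that the first part misses effects that persist off stimulation and that the second mixes lasting effect with drift.

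The cost is SAP wording and two more exploratory correlations per disease group. These will be imprecise, and at n = 5 nearly uninformative. No new data are needed if an off recording is made at the 12-month visit. Objectives implies this, through on and off recordings at multiple time points and 12 months as a named chronic time point in hypothesis 2, but does not say it. The SAP should confirm whether that recording exists.

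### Correlation question 2 measures the benefit of DBS by PAC rather than by a clinical rating, so it has no motor outcome

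*Combined protocol and SAP*

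**What the plan says.** All the correlation text is in the combined protocol and SAP under Statistical Methods and Data Analysis.

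- The introductory sentence promises, within each disease group, the "correlation between these brain physiology measures, and clinical instruments used to measure the motor benefit produced by DBS".
- Question 1 takes PAC before stimulation as predictor and asks about the "degree of benefit produced by DBS (difference between clinical ratings at 12 months on stimulation and baseline pre-implantation, off medication").
- Question 2 takes as predictor the change in PAC between the pre-stimulation recording and the 12-month on-stimulation recording. It asks whether that change would "correlate with the degree of benefit produced by DBS (difference between PAC on-stimulation, off medication").

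Under Objectives, hypothesis 3 reads "DBS-induced changes in abnormal cortical oscillatory activity may predict the degree of DBS-induced improvement in motor function". The Efficacy Assessments row lists clinical scales only: UPDRS and dyskinesia scales for PD, BFMDRS and TWSTRS for dystonia, and global impression scales for all patients. The planned groups are "10 PD; 5 dystonia".

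**The concern.** Two consecutive questions use the same phrase for DBS benefit and give it incompatible definitions. In question 2 the outcome is a physiological measure, the same one that forms the predictor. The parenthesis also names only one side of a difference and gives no time point, so it does not define a variable that can be computed.

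Question 2 is the only correlation written out that links a change in cortical activity to benefit, which is the content of hypothesis 3. Question 1 uses a pre-stimulation level, not a change. The add-on questions compare clinical states and do not correlate change with benefit. The introductory sentence would allow other correlations, but none is specified. If PAC stands on both sides, a non-zero correlation can arise from the shared term and say nothing about motor function. The plan expects these exploratory results to shape what follows: "it is anticipated that the next phase of the study will focus on a subset of the research aims".

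**Working it through.** **Comparison of the definitions**

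| Place | Physiology side | Benefit side |
|---|---|---|
| Introductory sentence | Brain physiology measures | Clinical instruments |
| Question 1 | PAC before stimulation | Clinical ratings, 12 months on stimulation against pre-implantation, off medication |
| Question 2 | PAC change, 12 months on stimulation against pre-stimulation | PAC on stimulation, off medication; second term and time point absent |
| Hypothesis 3 | Change in cortical oscillatory activity | Improvement in motor function |

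Three of the four rows put a clinical or motor quantity on the benefit side. Question 2 does not. The section itself describes PAC as an index of cortical synchronization, and PAC is not among the efficacy assessments.

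**Illustration of the consequence**

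The plan has no figure to reproduce here: it states no alpha, test or effect size for these correlations. From the documents come only the group sizes, 10 and 5. Assumed: bivariate normal PAC values, a Pearson test at two-sided 0.05, and a correlation rho between the two PAC visits.

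Let P0 be pre-stimulation PAC with SD s0, and P12 be 12-month on-stimulation PAC with SD s12. The predictor is P12 − P0.

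*Reading A:* the benefit is the same PAC change. Then r = 1 by construction.

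*Reading B:* the benefit is P12 alone. Then

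corr(P12 − P0, P12) = (s12 − rho·s0) / √(s12² + s0² − 2·rho·s0·s12).

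With s12 = s0 this reduces to √((1 − rho)/2); for example, rho = 0.5 gives √0.25 = 0.50. The critical |r| is t/√(n − 2 + t²), which is 0.632 at n = 10 and 0.878 at n = 5. Rejection rates come from 200,000 simulated samples per cell:

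| rho | Built-in r | p < 0.05 at n = 10 (PD) | p < 0.05 at n = 5 (dystonia) |
|---|---|---|---|
| 0 | 0.71 | 69% | 28% |
| 0.3 | 0.59 | 47% | 18% |
| 0.5 | 0.50 | 33% | 13% |
| 0.7 | 0.39 | 20% | 9% |
| 0.8 | 0.32 | 14% | 8% |

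The sign reverses if suppression is coded as pre-stimulation minus on-stimulation.

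The result depends on the variance ratio. At rho = 0.7:

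- s12/s0 = 0.5: (0.5 − 0.7)/√(0.25 + 1 − 0.70) = −0.27, with rejection in 12% of samples at n = 10 and 7% at n = 5
- s12/s0 = 0.7: r = 0, with rejection at the nominal 5%
- s12/s0 = 1.0: r = 0.39
- s12/s0 = 1.3: (1.3 − 0.7)/√(1.69 + 1 − 1.82) = 0.64

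For comparison, a simulated clinical change unrelated to PAC (20,000 samples per cell; rho = 0, 0.5 and 0.7) gave p < 0.05 in 4.8% to 5.0% of samples at n = 10 and 4.9% to 5.3% at n = 5.

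**The case against.** The strongest reply is that the intent is plain. The introductory sentence governs the questions beneath it, and question 1 defines the same phrase by clinical ratings. Since the parenthesis in question 2 cannot be computed as it stands, an analyst would have to go back to that sentence or to the sponsor. This stands, and it is why the point is a correction rather than a serious design flaw. It does not make the written definition right.

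Second, the illustration rests on assumed inputs and on one of several readings, and its correlation runs from −0.27 through 0 to 0.71. This also stands. The figures show what could follow; the text alone establishes the error.

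Third, the text may have been damaged when the PDF was read, since the add-on question nearby is garbled. That cannot be excluded, but the wording at question 2 is continuous, with no gap or redaction mark, so it remains conjecture.

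Fourth, this is a small pilot. The plan concedes that its numbers may not settle every question, has no sample size derivation, and attaches no decision rule to this result. That limits the severity and is accepted. Finally, naming a single scale per disease is a separate matter that applies equally to question 1. That is fair; the main correction does not depend on it.

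**Conclusion.** The concern holds. Question 2 is wrong as written: its outcome is PAC, it lacks a second term and a time point, and it conflicts with the introductory sentence, question 1 and hypothesis 3. Confidence is high because the conclusion rests on the documents' wording alone. It should be fixed. The effect is confined to one exploratory question, and no sample size, stated error rate or safety procedure is affected. How large a spurious correlation would be cannot be determined from the documents: under the stated assumptions it may be substantial, zero or reversed in sign.

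**What to change.** Replace the outcome parenthesis in question 2 with the one already used in question 1: "difference between clinical ratings at 12 months on stimulation and baseline pre-implantation, off medication". Keep PAC on the predictor side only, and have the sponsor confirm that this is the contrast intended.

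Two additions would help both questions but are secondary. First, name one planned scale per disease group before analysis. For PD, UPDRS part III is the natural choice, since it is the only scale whose medication state the plan describes ("UPDRS part III will be scored on and off of" antiparkinsonian medications). For dystonia, choose either BFMDRS or TWSTRS and state what off medication means there, because the documents do not say in which medication state those scales are scored. Second, state the sign convention for suppression and for benefit.

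The cost is one or two sentences of SAP wording. The scales are already planned and question 1 already calls for the same clinical contrast, so the main correction asks for no data beyond those question 1 needs.
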